7. SCHEDULE OF ASSESSMENTS

The study flow chart, including all procedures to be performed during the study is presented below. Prior to engaging in any study procedure, each subject must sign and date an informed consent form. In addition, a telephone contact will take place as footnoted below to find out if any treatment related problems have occurred. Additional telephone calls to the subjects for treatment follow-ups of AEs will be made as needed.

Evaluation	Enroll ^a	Treatment Period ^c		
		1	2	3 ^b
Site Visit ^h	1	2	3 ^b	4/ET ^c
Study Week(s)	1	13±2	26±2	39±2
Informed Consent ^a	X			
Inclusion/Exclusion	X			
Concurrent Medications		X	X ^{b#}	X
Physical Exam			X ^b	X
Vital Signs ^d		X	X ^{b#}	X
Safety Laboratories ^f			X ^b	X
Urine Pregnancy test ^{fg}		X	X ^b	X
Urinalysis ^f			X ^b	X
12-lead electronic ECG			X ^b	X
Drug Dispensed/returned	D	D/R	D [#] /R ^{b#}	R
Adverse Event Assessments		X	X ^{b#}	X

^aThe Informed Consent Form (ICF) must be signed before any protocol procedures are performed.

^bThis is the final visit for subjects that enrolled from Protocol TEN-01-302 and only procedures with this footnote are performed on subjects from TEN-01-302. Procedures for subjects enrolled from Protocol TEN-01-301 are marked with a #

^cThis is the final visit for subjects that enrolled from Protocol TEN-01-301. It is also used as an early termination (ET) visit.

^dVital signs include systolic and diastolic blood pressure (seated), heart rate, respiratory rate, temperature and body weight.

^eWhen a subject discontinues early, procedures performed at Visit 4 should be performed at the subject's last visit.

^fLaboratory assessments are detailed in Appendix A

^g If the urine pregnancy test is positive, it will be confirmed with a serum pregnancy test.

^hTelephone calls will be made to subjects monthly during the two months prior to a site visit to ascertain if there have been any treatment related problems (Weeks 5±1, 9±1, 17±1, 22±1 for subjects from TEN-01-301 and TEN-01-302 and for subjects from TEN-01-301 also Weeks 30±1 and 35±1).

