10.7.5 Safety Analyses

Safety assessments will be based on the incidence, severity, and type of adverse events, and clinically significant changes in the subject's clinical laboratory tests, vital signs, ECGs and physical examinations.

Adverse events will be coded using the MedDRA adverse event coding system for purposes of summarization. All adverse events reported will be listed in the data listings. Treatment emergent adverse events (TEAEs) will be tabulated for each treatment cohort and overall, where treatment emergent is defined as any adverse event which occurs after administration of the first dose of study drug and up through the final visit (Visit 3 for subjects from TEN-01-302 and Visit 4 for subjects from TEN-01-301), any event that is considered drug-related regardless of the start date of the event, or any event that is present at baseline but worsens in severity or is subsequently considered drug-related by the investigator. TEAEs will also be tabulated by whether events are considered related to treatment (possibly or probably drug-related, or unknown in relationship) and by severity. Serious adverse events and TEAEs resulting in study discontinuation will be tabulated.

Actual values and change from baseline values for clinical laboratory tests (including urinalysis) will be summarized at each visit collected during the study for each treatment cohort and overall. The frequency of clinically significant abnormal laboratory test values will be tabulated by treatment cohort and overall. Shift tables will be derived for changes in laboratory tests from the last values obtained during TEN-01-301 or TEN-01-302 to Visit 3 or 4.

Vital signs will be summarized descriptively for actual values and change from baseline values by visit and treatment cohort as well as overall. Vital signs are collected at study visits 2, 3 and 4, as applicable. Baseline for the vital signs will be the last values obtained during TEN-01-301 or TEN-01-302.

12-lead electrocardiogram (ECG) results will be summarized descriptively for actual values and change from baseline values by treatment cohort and overall for each visit (Visit 3 or Visit 4 as applicable). Baseline for the ECG will be the last values obtained during TEN-01-301 or TEN-01-302. The overall interpretation will be

summarized with number of subjects and percentages for the normal and abnormal ECG result categories.

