2.2.3 Duration of Study

For each subject, the entire study will last for a total of approximately 52 to 55 weeks; including completion of either the TEN-01-301 or TEN-01-302 studies. For subjects completing studies TEN-01-301 or TEN-01-302, TEN-01-303 treatment duration will be 39 and 26 weeks, respectively. The study flow chart, including all procedures to be performed during the study is presented below.

SCHEDULE OF ASSESSMENTS FOR THE STUDY

The study flow chart, including all procedures to be performed during the study is presented below. Prior to engaging in any study procedure, each subject must sign and date an informed consent form. In addition, a telephone contact will take place as footnoted below to find out if any treatment related problems have occurred. Additional telephone calls to the subjects for treatment follow-ups of AEs will be made as needed.

Evaluation	Enroll ^a	Treatment Period		
		1	2	3 ^b
Site Visit ^h	1	2	3 ^b	4/ET ^c
Study Week	1	13±2	26±2	39±2
Informed Consent ^a	X			
Inclusion/Exclusion	X			
Concurrent Medications		X	X ^{b#}	X
Physical Exam			X ^b	X
Vital Signs ^d		X	X ^{b#}	X
Clinical Laboratory Tests ^f			X ^b	X
Urine Pregnancy test ^{fg}		X	X ^{b#}	X
Urinalysis ^f			X ^b	X
12-lead ECG			X ^b	X
Drug Dispensed/returned	D	D/R	D [#] /R ^{b#}	R
Adverse Event Assessments		X	X ^{b#}	X

^a The Informed Consent Form (ICF) must be signed before any protocol procedures are performed.

^b This is the final visit for subjects who enrolled from Protocol TEN-01-302 and only procedures with this footnote are performed. Procedures for subjects enrolled from Protocol TEN-01-301 are marked with a #.

^c This is the final visit for subjects who enrolled from Protocol TEN-01-301.

^d Vital signs include systolic and diastolic blood pressure (seated), heart rate, respiratory rate, temperature and body weight.

^e When a subject discontinues early, procedures performed at Visit 4 should be performed at the subject's last visit.

^f Laboratory assessments are detailed in Appendix A of the protocol.

^g If the urine pregnancy test is positive, it will be confirmed with a serum pregnancy test.

^h Telephone calls will be made to subjects monthly during the two months prior to a site visit to ascertain if there have been any treatment related problems (Weeks 5±1, 9±1, 17±1, 22±1, for subjects from TEN-01-301 and TEN-01-302 and for subjects from TEN-01-301 also Weeks 30±1 and 35±1).

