3. STATISTICAL METHODOLOGY

3.1 Determination of Sample Size

Based on the two Phase 3 studies (TEN-01-301 and TEN-01-302) and the different treatment arms, 300 subjects entered into this open label long-term safety study should produce approximately 150 subjects with at least 52 weeks exposure to tenapanor 50 mg BID and an additional 150 subjects with 26 to 39 weeks of exposure to tenapanor 50 mg BID.

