3.2 Analysis Sets

Safety Analysis Set: All subjects who receive at least one dose of study drug will be included in all analyses of safety data.

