3.5 Visit Windows

Observed data will be used for the safety analyses. No visit windows will be applied.

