3.6.4 Study Drug Exposure and Compliance

Days of exposure to study drug will be summarized with descriptive statistics by treatment cohort and all subjects overall. In addition, a contingency table will be provided to display the number and percentage of subjects in each treatment cohort and overall with exposure in the following categories: ≤ 13 weeks, >13 to ≤ 26 weeks, and >26 weeks.

Days of possible exposure is defined as:

$$\text{date of last dose of study drug} - \text{date of first dose of study drug} + 1.$$

When the last known dose date is missing, the last known clinic visit date during the treatment period will be used, and the plus 1 will be removed from the calculation.

Summary statistics will also be presented for percent compliance to study drug. The percent compliance to study drug will be calculated as the total number of tablets dispensed minus the total number of tablets returned divided by two times the number of days during the treatment period, then multiplied by 100.

Summary statistics will be presented for percent compliance to study drug by treatment cohort and overall. The count and percentage of subjects with overall compliance $<80\%$, $80\%-100\%$, and $>100\%$ will also be tabulated by treatment cohort and overall.

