3.7.2 Clinical Laboratory Tests

The list of clinical laboratory tests collected during this study is presented in Appendix A of the protocol. Serum chemistry, hematology, and urinalysis results will be summarized with descriptive statistics at Enrollment (based on the last values obtained during TEN-01-301 or TEN-01-302), and Visit 3 (for subjects enrolled from TEN-01-302) or Visit 4 (for subjects enrolled from TEN-01-301) by treatment cohort and overall. For continuous tests, actual values and change from enrollment will be summarized. For categorical tests, the number and percentage of subjects in each category will be presented for each visit. Serum chemistry tests included in these summaries will be albumin, alkaline phosphatase, ALT, AST,

bicarb/CO₂, total bilirubin, direct bilirubin, indirect bilirubin, calcium, chloride, total cholesterol, creatinine, glucose, inorganic phosphorous, LDH, potassium, total protein, sodium, triglycerides, BUN/urea, and uric acid. Hematology tests included in these summaries will be WBC, RBC, MCV, MCH, MCHC, hemoglobin, hematocrit, and platelet count. Differentials consisting of bands, monophils, neutrophils, eosinophils, lymphocytes, and basophils will be included in the listings only. Urinalysis tests included in these summaries will be appearance, specific gravity, and pH. Protein, glucose, ketones, blood, nitrite, and microscopic results will be presented in listings only.

The frequency of clinically significant abnormal laboratory test values will be tabulated by treatment cohort and overall.

Shift tables classifying normal range results (low out of normal range, normal, or high out of normal range) between enrollment and the final visit will be tabulated by treatment cohort and overall. Missing results for each pairwise summary will be tabulated.

Data listings of clinical laboratory tests will include flags for abnormal results.

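### Does SAP 3.7.2 need a rule for where early termination laboratory values are summarised?

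*SAP*

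**What the plan says.** Protocol 8.2.1.5 has chemistry, hematology and urinalysis samples taken at Visit 3 for subjects from TEN-01-302, at Visit 4 for those from TEN-01-301, and at any early termination visit. The schedule in both documents has one column, headed 4/ET, at Week 39±2. Footnote c in Protocol Section 7 says of Visit 4: "It is also used as an early termination (ET) visit". The SAP's footnote c stops at "This is the final visit for subjects who enrolled from Protocol TEN-01-301", although the SAP keeps the 4/ET heading and footnote e, under which anyone who discontinues early has the Visit 4 procedures at the last visit.

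On analysis, SAP 3.7.2 places laboratory summaries at enrollment and at "Visit 3 (for subjects enrolled from TEN-01-302) or Visit 4 (for subjects enrolled from TEN-01-301) by treatment cohort and overall". Its shift tables run from enrollment to the final visit, with no mention of early termination. SAP 3.5 states: "Observed data will be used for the safety analyses. No visit windows will be applied". SAP 3.3 rules out carrying values forward. SAP 3.2 reads: "All subjects who receive at least one dose of study drug will be included in all analyses of safety data". Protocol 10.7.5 is broader than SAP 3.7.2: laboratory values and changes "will be summarized at each visit collected during the study for each treatment cohort and overall".

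**The concern.** Safety is the only objective, and each subject has one scheduled set of bloods. Protocol Table 8-1 allows one hematology and one chemistry sample (3 + 7 = 10 mL). For someone who stops early, the early termination sample is therefore the only scheduled on-study laboratory result.

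Read by visit label, SAP 3.7.2 seems to treat such results differently by parent study. The change summary for TEN-01-302 would describe completers only. The summary for TEN-01-301 would mix completers with people sampled much earlier. The shift tables could count an early stopper from TEN-01-302 as missing although a result exists. The SAP plainly expects early stoppers: SAP 3.6.4 plans a table "to display the number and percentage of subjects in each treatment cohort and overall with exposure in the following categories", and the lowest category (13 weeks or less) lies below the earliest scheduled end of treatment, Week 24. It gives no matching rule for their labs.

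**Working it through.** **Where each subject's labs go.** The SAP applies no windows and carries nothing forward, so the row depends on how the early termination (ET) visit is coded and how SAP 3.7.2 is read.

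| Subject | ET coded as Visit 4, literal reading | ET has its own code, literal reading | One end-of-treatment value per subject |
|---|---|---|---|
| TEN-01-302 completer | Visit 3 row | Visit 3 row | included |
| TEN-01-301 completer | Visit 4 row | Visit 4 row | included |
| TEN-01-302 early stopper | no row | no row | included if ET counts |
| TEN-01-301 early stopper | Visit 4 row, at any week | no row | included if ET counts |

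The difference between parent studies appears only in the first reading. The third has support in the protocol: 8.1.3 calls Visit 3, and 8.1.4 calls Visit 4, the end of treatment visit for the respective parent study. Under that reading the only open question is whether ET counts.

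**Number of tests.** SAP 3.7.2 names 21 chemistry + 8 hematology + 3 urinalysis = 32 tests for summary. Change is summarised for continuous tests only, and urinalysis appearance is categorical, so at most 32 − 1 = 31 tests have a change row.

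**Timing in the Visit 4 row (first reading only).** The windows are 26 ± 2 = Weeks 24 to 28 for Visit 3 and 39 ± 2 = Weeks 37 to 41 for Visit 4. An ET draw before the Visit 4 window lies between 39 − 36 = 3 and 39 − 1 = 38 weeks before Week 39. Suppose a fraction *d* of TEN-01-301 subjects stops at week *t*, all of them are sampled, and completers are sampled at Week 39. The mean sampling week of the row is then 39 − *d*(39 − *t*), which falls below 37 when *d* > 2/(39 − *t*):

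- *t* = 6: 2/33 = 6.1%
- *t* = 13: 2/26 = 7.7%
- *t* = 26: 2/13 = 15.4%

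Both *d* and *t* are assumptions. The result describes when the samples were taken and says nothing about any laboratory value. Week 37 is a limit for individual visits, so using it as a benchmark for a mean is arbitrary.

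**Number of subjects.** The documents do not give it. SAP 3.1 says 300 entered subjects "should produce approximately 150 subjects with at least 52 weeks exposure to tenapanor 50 mg BID and an additional 150 subjects" with shorter exposure. Since 150 + 150 = 300, no dropout allowance is visible. If 10% to 30% of 300 stopped early and all were sampled, that would be 30 to 90 subjects across both parent studies, with an unknown split.

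**Outputs that do not depend on the row.** The count of clinically significant abnormal values in SAP 3.7.2 is not tied to a visit. The listings carry every result with abnormal flags. Protocol 9.6 requires a clinically relevant laboratory deterioration to be recorded as an adverse event, so it also reaches the adverse event tables.

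**Other assessments.** SAP 3.7.3 (vital signs, ECG) and 3.7.4 (physical examination) do not limit Visit 4 by parent study. Under Visit 4 coding, an early stopper from TEN-01-302 fits the Visit 4 row there. What remains is that early-drawn values share that row.

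**The case for a change.** The case for a change is that the gap is real and cheap to close. SAP 3.7.2 is narrower than Protocol 10.7.5, and its limit by parent study is what could leave a TEN-01-302 early stopper without a row. Protocol 8.2.1.4 takes Visit 4 vital signs from TEN-01-301 subjects and early terminations, which supports coding ET as Visit 4. Vital signs and labs from the same ET visit could then be handled differently. Where the SAP explains the term final visit, in its definition of treatment-emergent events (3.7.1), it names only Visits 3 and 4, so the shift tables are unclear too. One sentence would settle all of this.

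Much of that stands: the text does not assign ET labs, and the shift-table endpoint is open. The argument for harm is weaker. SAP 3.2 defines who is in the analysis set; it does not promise each subject a value in every by-visit row, so there is no contradiction with it. Protocol Section 10 expressly lets the SAP change the statistical section, so being narrower than 10.7.5 is not an error. The SAP's shorter footnote c carries little weight beside the 4/ET heading and footnote e, which it retains.

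**Conclusion.** No change to the plan follows. SAP 3.7.2 leaves a detail unstated that analysts ordinarily settle in table shells and programming specifications. Protocol Section 10 provides for shells, and SAP Section 4 has the specifications finalised before database lock. Neither was available for this review, so whether they already settle it is unknown.

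At its widest, the gap touches descriptive value and change summaries for at most 31 continuous tests, and possibly the shift tables, for early stoppers only. That extent requires a literal reading of the parent-study limit. The contrast between TEN-01-302 and TEN-01-301 requires, in addition, that ET be coded as Visit 4. No hypothesis is tested. SAP 3.7 bases the safety assessment on adverse events and clinically significant changes, and the tables that carry these do not depend on the row assignment. The safety conclusion would be sound under any of the readings. This judgement assumes that ET samples are entered in the database and listed, as the protocol requires. It does not rest on a particular dropout rate.

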3.7.3 Vital Signs and 12-lead Electrocardiogram

Vital signs (body weight, heart rate, respiratory rate, sitting systolic blood pressure, sitting diastolic blood pressure, and temperature) will be summarized descriptively for actual values and change from enrollment values by treatment cohort and overall by visit. Enrollment values for the vital signs will be the last values obtained during TEN-01-301 or TEN-01-302.

Electrocardiogram results (heart rate, PR interval, QRS duration, QT, QTcB and QTcF intervals) will be summarized descriptively for actual values and change from enrollment values by treatment cohort, overall, and visit. Enrollment values will be obtained in a similar manner as for the vital signs. The overall interpretation will be summarized with number of subjects and percentages for the normal and abnormal ECG result categories.

All vital signs and electrocardiogram results will be listed. Abnormal or clinically significant results will be flagged.

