3.7 Safety Analyses

Safety assessments will be based on the incidence, severity, and type of adverse events, and clinically significant changes in the subject's clinical laboratory tests, vital signs, ECGs, and physical examinations.

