3.7.4 Physical Examination

Physical examinations (general appearance, HEENT, respiratory, cardiovascular, abdomen, skin, lymph nodes, musculoskeletal, extremities, and neurological) will be summarized at enrollment (last values collected for TEN-01-301 or TEN-01-302), and at Visit 3 or Visit 4. The number and percentage of subjects in each category will be presented for each visit by treatment cohort and overall.

All physical examination results will be listed. Abnormal physical exam results will be flagged.

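### The ECG interpretation and physical examination tables give only category percentages at each time point, so they cannot show how many subjects became newly abnormal

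*SAP*

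**What the plan says.** SAP 3.7 bases the safety assessment on adverse events and on "clinically significant changes in the subject's clinical laboratory tests, vital signs, ECGs, and physical examinations". The four kinds of measurement stand there on an equal footing. The later sections treat them differently.

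- **Laboratory tests (SAP 3.7.2).** The frequency of clinically significant abnormal values is tabulated. There are also "Shift tables classifying normal range results (low out of normal range, normal, or high out of normal range) between enrollment and the final visit", with missing results counted for each pair.
- **ECG, numeric parameters (SAP 3.7.3).** Heart rate and the intervals "will be summarized descriptively for actual values and change from enrollment values by treatment cohort, overall, and visit". Vital signs are handled in the same way. Under SAP 3.6, continuous variables are shown with mean, standard deviation, minimum, median and maximum.
- **ECG, overall interpretation (SAP 3.7.3).** "The overall interpretation will be summarized with number of subjects and percentages for the normal and abnormal ECG result categories". SAP 3.6 presents summaries by visit, for each cohort and for all subjects. No cross-classification against enrollment is mentioned. All results are listed, and "Abnormal or clinically significant results will be flagged".
- **Physical examination (SAP 3.7.4).** Each body system has two time points: enrollment, taken from the end of the parent study, and one final visit. The content of the table is set out as follows: "The number and percentage of subjects in each category will be presented for each visit by treatment cohort and overall". Results are listed, and "Abnormal physical exam results will be flagged".

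**The concern.** A change in a subject needs that subject's enrollment result and later result side by side. The planned tables for the ECG interpretation and the physical examination give each time point separately. A subject who was abnormal at enrollment and stayed so counts the same at the final visit as one who has just become abnormal.

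Safety is the only objective, and there is no control arm and no testing (SAP 2.1 and 3.6). Change from enrollment is therefore the main internal comparison. For these two assessments, the tables would leave open how many subjects developed a new abnormality during the study.

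**Working it through.** The plan states no figure on this point, so there is none to reproduce. The check asks what the planned percentages determine.

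**Bounds on new abnormalities.** Take N subjects with results at both time points, A abnormal at enrollment and F abnormal at the final visit. Let x be the number who go from normal to abnormal and y the number who go from abnormal to normal. Then x − y = F − A, so the table fixes only the net difference. The number of new abnormalities satisfies

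max(0, F − A) ≤ x ≤ min(F, N − A).

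The documents give no abnormality rates, so the rates below are assumptions. N = 300 is the planned enrollment, treated for simplicity as fully paired.

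| Abnormal at enrollment, final | A, F | Range of x | Share of those normal at enrollment (N − A) |
|---|---|---|---|
| 5%, 5% | 15, 15 | 0 to 15 | 0 to 15/285 = 5.3% |
| 10%, 10% | 30, 30 | 0 to 30 | 0 to 30/270 = 11.1% |
| 20%, 20% | 60, 60 | 0 to 60 | 0 to 60/240 = 25.0% |
| 10%, 12% | 30, 36 | 6 to 36 | 6/270 = 2.2% to 36/270 = 13.3% |
| 20%, 15% | 60, 45 | 0 to 45 | 0 to 45/240 = 18.8% |

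With N = 150 and 20% at both time points, A = F = 30. Then x lies between 0 and 30, and 30/120 = 25%.

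**Different subjects in the overall column.** Under protocol 8.2.1.2 and 8.2.1.3, the physical examination and ECG are done at Visit 3 for subjects from TEN-01-302, at Visit 4 for those from TEN-01-301, and at any early termination visit. Overall, enrollment covers subjects from both parent studies, while Visit 3 and Visit 4 hold different subsets.

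Suppose 150 subjects come from each parent study, with 10% abnormal at enrollment (15) among those from TEN-01-302 and 20% (30) among those from TEN-01-301. Suppose also that nobody changes or leaves early. The overall column then reads:

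- enrollment: (15 + 30)/300 = 15%
- Visit 3: 15/150 = 10%
- Visit 4: 30/150 = 20%

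The percentages move although no subject has changed. Exchanging the two rates gives 15%, 20% and 10%. The split and the rates are assumptions. Within a single cohort this effect is mostly absent, because its completers share one final visit.

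**The case against.** The strongest reply is that clinically significant change is captured elsewhere. Protocol 9.6 makes any clinically relevant deterioration in a laboratory test or other clinical finding an adverse event, and SAP 3.7.1 counts subjects with treatment-emergent events by system organ class and preferred term. This stands, and it limits the point. It does not remove it. The same rule names laboratory tests, and the SAP still gives those shift tables. An adverse event table also does not identify an ECG or examination shift, or give the number who were normal to begin with.

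A reader might infer that individual changes in vital signs and ECG intervals are hidden behind means. The SAP does not support that. Change from enrollment is summarized with standard deviation, minimum and maximum, so the largest changes are visible. Only a count of subjects beyond a threshold is absent.

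A reader might also expect equal percentages to be taken as proof of no ECG effect. That is conjecture about a descriptive report. Enrollment values are the last from the parent study, and by the SAP 3.6 cohort table cohorts 1, 3 and 4 were on tenapanor in the last parent-study period. For them, even a shift table would not measure change from an untreated state. Dropout is a weaker worry than it may seem, because subjects who leave early should have the Visit 4 procedures.

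The flagged listings allow a count by hand, but the SAP does not say that they include parent-study results. SAP 4 leaves the list of tables to a separate programming document. Shift tables may be planned there, but the SAP text does not commit to them.

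**Conclusion.** The point holds for two outputs: the ECG overall interpretation and the physical examination. Their planned tables cannot give the number of newly abnormal subjects, and the overall column does not follow one set of subjects over time. In the illustrations with equal rates, the same table fits anything from no new abnormality to every final abnormality being new. The upper ends are extremes: they require every enrollment abnormality to resolve. They show what the table leaves open, not what is likely.

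This is a reporting gap. It does not threaten validity, and it affects no sample size, estimate or decision rule. The documents do not support the wider reading that clinically significant safety changes would go unreported.

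**What to change.** Keep the per-visit summaries, which protocol 10.7.5 also specifies, and add to SAP 3.7.3 and 3.7.4:

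1. A within-subject shift table, normal/abnormal, from enrollment to the final visit for the ECG overall interpretation. The final result is that of Visit 3, Visit 4 or early termination, whichever applies.
2. The same table for each body system in the physical examination.
3. Both by cohort and overall, with missing pairs counted as in SAP 3.7.2.
4. Abnormal ECGs split by clinical significance, and a count of subjects with newly clinically significant ECG or vital sign results, only where clinical significance was recorded at both time points. The documents do not show that it was. Investigator grading is described for laboratory tests alone (protocol 8.2.1.5), the ECG and vital sign flag is a combined one, and the examination flag covers only abnormality.

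The cost is a few extra tables on the laboratory template. No new visit or procedure is needed, because the SAP already summarizes both assessments at enrollment and afterwards. Protocol Section 10 lets changes to its statistical considerations be made in the SAP without a protocol amendment.
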